There is no agreement concerning the most appropriate criteria to be used. What is needed is a valid and accessible tool to establish the early identification and desirable management of nutritional risk in children. . There remains a great variation in the criteria used to define malnutrition, with each method having its own limitations.

Pre-existing paediatric nutrition screening tools

Recently a variety of nutritional screening tools have been developed for assessment of nutritional status of children in hospital setting, including; SGNA (Subjective Global Nutritional Assessment) (Secker and Jeejeebhoy, 2007), STAMP (Screening Tool for the Assessment of Malnutrition in Paediatric) (McCarthy H, et al. 2008 and More J, 2008),

STRONG kids (Screening Tool Risk on Nutritional Status and Growth) (Jessi M. Hulst et al., 2010), and PYMS (Paediatric Yourhill Malnutrition Score). These all use the internationally recognized predictors of undernutrition: clinical assessment, dietary intake and anthropometric measurements. Each of these components bears a nutrition risk score, and overall score corresponds to the overall undernutrition risk of the patient. Although, recent studies have attempted to develop appropriate nutritional screening tools for children on admission, they are not useful for infants as they have not been validated except of STRONG kids (Screening Too Risk on Nutritional Status and Growth) which has been developed for hospitalized children as well as infants.

Development of the infant Paediatric Yorkhill Malnutrition Score (iPYMS)

A project team, consisting of senior nursing, dietetic, research academic and medical staff have developed a preliminary tool that would be both simple and quick to use. The infant nutritional screening tool will consist of four fields;

1. Weight centile (using admission weight)
2. Poor weight gain (by parental report)
3. Reduced intake
4. Effect on nutrition of current illness

On admission this tool would be completed by the nurse (researcher initially). A score of 0 or 1 classify patient at a low and median risk of undernutrition and a score of 2 or more reflects a high risk of undernutrition.

Purpose of the Study

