The Paediatric Yorkhill Malnutrition Score (PYMS) for infants must be able to distinguish those who are well-nourished from those malnourished or at risk of becoming so. It is based on internationally recognized predictors or symptoms of undernutrition (weight gain, reduced dietary intake), and therefore has face validity. However we need to compare it with results of other reputable nutritional measurements (concurrent validity), and its diagnostic value to screen the same patients with other currently used methods of undernutrition has to be tested (criterion validity). Accuracy is also important, considering how well the tool performs in detecting infants who really have problems and correctly identifying those who do not (sensitivity and specificity). So, we need further measurements to consider its sensitivity and the discriminant validity of the tool. We will study all screen positive and a sample of screen negative infants, using skinfolds and previous weight measurements and a parentally completed eating behaviour questionnaire. We will use this data to test the utility of PYMS score, growth trajectory, body mass index and behaviour questionnaire as predictors of low adiposity and stunting.

The discriminant validity of the screening tool will be tested using body composition measurement using triceps (TSF) and subscapular skinfold thickness and the mid upper arm circumference (MUAC) and SGNA (Subjective Global Nutritional Assessment). To test the concurrent validity, the results from the infant screening tool will be compared with the results of STRONG kids (Screening Tool Risk on Nutritional Status and Grow).

Reliability is also essential as the tool must produce similar results with repeat testing in the same circumstances and with different users where the patient's state has not changed. User-group may affect tool performance; for example, whether doctors, nurses or dieticians conducted the screening. Thus, the reliability of the tool needs to be tested in future.

Subjects

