Participant of the study will be all patients newly admitted to selected wards (medical and general surgical wards) at the Royal Hospital for Sick Children (and possibly RAH Paisley). An average of 8 patients per day are admitted to the relevant wards and we will aim to recruit a total of 200 over a 4 month period, after an initial pilot with up to 20 patients. Children aged 1 -24 months are the subjects of this study because the purpose of this study is to develop a screening tool for infants.

Exclusions

- Patients in the short stay ward, intensive care or high dependency unit, Oncology unit, NICI and PICM, Cardiology (SA),
- Patient who have been transferred from neonatal units and PICM and NICM.

Sample Size- Power Calculation

Using the Altman monogram 45 subjects in each group (135 in total) would give 90% power to detect a difference of 0.66SD (1 centile space) in skinfolds between any two of the 3 groups. 70 subjects in each group (210) gives 80% power to detect a difference of 0.5SD in skinfolds between any two of the 3 groups.

It is likely that not all children will have complete measures so we will aim to recruit 200 subjects.

Sample Selection

Quota sampling will be used to obtain three equal groups of patients with different undernutrition scores (low, medium, high), until the desirable number of patients in each group is achieved. We will oversample high risk patients (expected to be only 10-20% of all patients) if necessary by screening all eligible patients using iPYMS and proceeding to full assessment for only those scoring high risk. In other word. a) The majority of patients screened at high risk of undernutrition. b) Every third child screened at medium risk of undernutrition. c) Every tenth child screened at low risk of undernutrition (Gerasimidis K et al, 2010).

We expect that malnutrition will be identified in between 10-30% of infant studied. If previously unrecognised this means they can then be referred for further assessment.

Recruitment

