The researcher will identify those patients eligible for screening by visiting the wards daily and obtaining details of new admissions from the nursing staff. She will then give an information leaflet to the patient's carer to read and answer any immediate questions. After at least one hour she will return to the ward and if the carer is happy to participate, the researcher will ask him/her to complete a consent form. A copy of the consent form will be given to the carers and another will be placed in the child's medical notes.

The material will be in written in a form suitable for anyone who can read English. We will not be able to include those infants where neither carer was able to read English.

Due to short admission periods usually most of the children will be discharged during the first day of stay. We aim to complete assessment on the next day after admission

Outcome Measurements

Parental questionnaires

1. Global Nutritional Assessment for infants (SGNA)

The researcher will ask the main carers of patients to complete the eating behavior questionnaire about the infant's diet (type of milk, supplementary feeding and weaning diet), weight loss (poor weight gain), gastrointestinal symptoms, and daily activity. A rough visual assessment of the child's muscle stores and fat will be carried out by the researcher. This is a global nutritional assessment procedure recently validated in paediatric patients as a measure of current and future nutrition risk (Secker & Jeejeebhoy, 2007). A copy of the assessment form and the article that describes this method is attached for the ethics committee attention.

2. Infant EBQ

This questionnaire has been developed using population data from a cohort study and is designed to identify infants at risk of weight faltering. This will be completed by the main carers of patients to assess the patient's general appetite and eating behaviour

Measurements

3. Triceps (TSF) and subscapular skinfold thickness

Measurement of the thickness of the skin of the arm (triceps) and shoulder blade (subscapular) will be done as a measure of fat store. Briefly the parent will take off their top clothing and the researcher will measure the skinfold thickness with Holtain calipers. This measurement will be to some extent inconvenient for patients particularly those who are <1 year of age.

4. Weight and length

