Weight will have been measured on admission. The researcher will re weight and measure length using the ward scales and recumbents stadiometer or our own portable equipment.

5. Mid upper arm circumference (MUAC)

The researcher will measure the circumference of their mid upper arm using a simple measuring tape.

6. Bioelectrical impedance (BIA)

This has been developed for assessment of nutritional status in children based on indices of lean and fat adjusted for body size (Wright CM et al, 2008). We want to discover whether this method is practical and effective in this young age range and how it relates to nutrition score. Self adhesive electrodes are attached to the right wrist and ankle while the child lies on the bed. Three reading are taken, while, the electrodes are attached

The infants may become briefly upset by being measured. If they become very upset and uncooperative that measurement will be abandoned.

Additional elements

7. STRONG kids (Screening Tool Risk on Nutritional Status and Growth)

The researcher will extract equivalent items for SGNA about the child's food intake, diarrhoea, vomiting, weight loss or poor weight gain or no weight gain, during the few days before admission. An observational assessment of patients will be also carried out by researcher in terms of diminished subcutaneous fat, muscle mass and hollow face (subjective clinical assessment- the same as b). In addition, the researcher will use information recorded in the medical notes of the patient to assess patients' underlying illness with a risk of malnutrition (Anorexia nervosa, Celiac disease, Cystic fibrosis, cardiac disease, and trauma).

8. Length of hospital stay (LOS)

Length of hospital stay as a secondary outcome will also be collected from hospital admissions statistics or through the notes.

9. Growth trajectory

Patients' birth weight will be collected by the maternal report in order to calculate weight trajectory.

Analysis-Statistics

Data will be entered into the electronic database of SPSS v15. The paper data will have names and dates of birth recorded in order to allow linkage to hospital discharge data. The electronic data will have only enough personal information to link it uniquely with the paper record. The anonymised electronic data will be stored on the password protected university network.

The raw measurements of body composition, height, weight. Skinfolds and mid upper arm circumference will be converted into standard deviation scores.

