- Height and weight will be converted into standard deviation scores according to the UK 1990 reference data.
- Skinfolds and mid upper arm circumference will be converted into standard deviation scores according to the World Health Organization reference values. A value less than -2 standard deviation scores denotes a patient at high risk of undernutrition.

Patient iPYMS outcome (nutrition risk), will be cross-tabulated with the respective nutrition risk from the Paediatric Subjective Global Nutrition Assessment or, body composition assessment. The proportion of patients at risk of undernutrition (according to body composition assessment and/or the Paediatric Subjective Global Nutrition Assessment) who were not identified by the iPYMS will be recorded as false negatives. On the contrary, the proportion of patients at low risk of undernutrition (according to body composition assessment and/or the Paediatric Subjective Global Nutrition Assessment) who were screened as at high risk of undernutrition by the iPYMS will be recorded as false positives.

The mean values per group compared using t-test and anova and the categorical data compared using chi squared and logistic regression analysis.

We will use this data to test the utility of PYMS score, growth trajectory, body mass index and behaviour questionnaire as predictors of low adiposity and stunting
K-statistics will be used for Agreement of the methods.

References

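### Growth trajectory is to be tested as a predictor, but the only pre-admission weight collected is maternally reported birth weight, which makes it a coarse measure in older infants

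*Protocol*

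**What the plan says.** The validity paragraph of the Method section says that infants will be studied "using skinfolds and previous weight measurements and a parentally completed eating behaviour questionnaire". It gives no source, number or dates for the earlier weights. Method and Analysis-Statistics both state that the data will be used to "test the utility of PYMS score, growth trajectory, body mass index and behaviour questionnaire as predictors of low adiposity and stunting".

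The weights actually listed for collection are these:

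- **Measurements, item 4:** "Weight will have been measured on admission", and the researcher then weighs the child again.
- **Recruitment:** "We aim to complete assessment on the next day after admission", so the repeat weight comes about one day after the first.
- **Additional elements, item 9 (Growth trajectory):** "Patients' birth weight will be collected by the maternal report in order to calculate weight trajectory".

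Recent weight change is otherwise recorded only by report. The second iPYMS field is "Poor weight gain (by parental report"). The SGNA asks the carer about weight loss or poor gain. The STRONG kids item covers "weight loss or poor weight gain or no weight gain, during the few days before admission". On age, the Subjects section says: "Children aged 1 -24 months are the subjects of this study".

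**The concern.** Method speaks of earlier weights in the plural, while item 9 supplies a single recalled value. Because the admission weight and the re-weigh are a day apart, trajectory reduces to a two-point contrast: reported birth weight against current weight, over an interval equal to the child's age.

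This is a question of what is collected, so a later analysis plan cannot repair it. A weight between birth and admission that is not copied down at the visit cannot be recovered by any formula.

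What is at stake is how well trajectory is tested as a predictor alongside the iPYMS score, body mass index and the behaviour questionnaire. If it performs poorly, the reader will not know whether growth history is uninformative or was only coarsely measured. In addition, poor recent gain reaches iPYMS, SGNA and STRONG kids by report, so no measured earlier weight stands as an independent check on it.

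**Working it through.** The protocol states no figure on this point, so there is none to reproduce. The check has two parts.

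**1. Text comparison**

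| Role | What the protocol provides | Section |
|---|---|---|
| Earlier weights intended | Plural, source and dates not given | Method |
| Earlier weights collected | Birth weight, maternal report | Additional elements, item 9 |
| Current weights | Admission and researcher's re-weigh, about 1 day apart | Measurements, item 4; Recruitment |
| Interval covered by trajectory | 1 to 24 months, equal to age | Subjects |

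No item collects a weight dated between birth and admission.

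**2. How much of the interval is recent?**

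The protocol defines no recent window; assume 2 months. The share of the birth-to-admission interval is min(1, 2/age):

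| Age (months) | 1–2 | 3 | 6 | 12 | 18 | 24 |
|---|---|---|---|---|---|---|
| Share | 100% | 67% | 33% | 17% | 11% | 8% |

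A rise of 0.67 SD followed by a recent fall of 0.67 SD gives a net change of 0.67 − 0.67 = 0, the same as steady growth. In the youngest infants the contrast is itself the recent change.

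**3. Illustration of size, on assumed correlations**

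The correlation r between earlier and admission weight SD scores is not in the protocol. Assume 0.4–0.6 from birth and 0.85–0.95 from a weight a few months earlier. Assume also SD scores with unit variance, normality, and a cut-off giving 5% false positives (z = 1.645). Recall error is not modelled.

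- Simple change: SD = √(2(1 − r)). Detection of a true 1 SD loss = Φ(1/SD − 1.645).
- Change conditional on the earlier score: SD = √(1 − r²), with the same detection formula.

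| r | SD, simple | Detection, simple | SD, conditional | Detection, conditional |
|---|---|---|---|---|
| 0.40 | 1.095 | 23% | 0.917 | 29% |
| 0.50 | 1.000 | 26% | 0.866 | 31% |
| 0.60 | 0.894 | 30% | 0.800 | 35% |
| 0.85 | 0.548 | 57% | 0.527 | 60% |
| 0.90 | 0.447 | 72% | 0.436 | 74% |
| 0.95 | 0.316 | 94% | 0.312 | 94% |

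With simple change from birth, the proportion of non-faltering infants who fall by more than 1 SD is Φ(−1/SD): 18.1%, 15.9% and 13.2% for r = 0.4, 0.5 and 0.6. Regression to the mean alone moves an infant born at +1.33 SD by 1.33(r − 1), which is −0.80 at r = 0.4 and −0.53 at r = 0.6.

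Conditioning on birth weight removes the regression-to-the-mean shift but raises detection only from 23–30% to 29–35%. On these assumptions, most of the gap to a more recent weight comes from which weight is collected.

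**The case against.** The strongest reply is that the protocol never asks trajectory to show recent faltering. It is one of several predictors of low adiposity and stunting, and net change since birth is a reasonable, if coarse, predictor of those. Birth weight is also a previous weight, so Method and item 9 are loosely matched rather than contradictory. Trajectory appears in none of the five listed hypotheses and sits under Additional elements. All of this stands, and it limits the point to a secondary analysis.

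A reader might go further in four ways that the document does not support:

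- **That the trajectory aim cannot be met.** It can: the change is computable and testable, only more weakly.
- **That recent faltering is invisible.** At about 1 to 3 months, birth to admission is largely the recent period, and at any age a recent fall still lowers the net change. The protocol gives no age distribution.
- **That a quarter of iPYMS goes unverified.** The protocol lists four fields but no points per field, and it sets out to validate the total score, not single items.
- **That iPYMS will be made to look better overall.** Any such effect is confined to the side-by-side comparison of predictors, and even there it is an inference.

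The size is also open to challenge. Every correlation is assumed, and a single low range for birth weight at all ages is unfair to the youngest infants, for whom birth was only a few months earlier. Regression to the mean depends on how change is defined, and the protocol gives no formula; that can properly be left to an analysis plan. What remains after these objections is that intermediate weights must be recorded at the visit or they are lost.

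**Conclusion.** The point holds as a weakness in data collection for a secondary predictor. Method points to earlier weight measurements, and item 9 delivers one reported birth weight. In older infants the resulting trajectory cannot place a change in time or distinguish early channel-settling from later loss; it carries recall error; and if analysed as a simple difference it is affected by regression to the mean.

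The main results do not depend on it: the cross-tabulations against SGNA and body composition, the skinfold comparison between risk groups, and the agreement with STRONG kids are unaffected.

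The detection figures (about 29–35% from birth with conditioning, against 60–94% from a more recent weight) are illustrations under the assumed correlations, not estimates for this population. The textual mismatch and the inability of two points to date a change need no such assumption.

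**What to change.** In item 9, record with its date any earlier weight found in the medical notes, which the researcher already consults for underlying illness and possibly for length of stay, or in a carer-held record if one is available. Keep reported birth weight as the fallback, and note the source of each weight. Analyse trajectory as the change in weight SD score conditional on the earlier score and on the interval.

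The cost is a few extra fields at the same visit, with no new procedure or staff. The yield is unknown: the protocol does not say that the notes hold earlier weights and does not mention a carer-held record, so some infants will have birth weight only. The change has to be made before data collection.

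If earlier weights will not be collected, reword the Method section to say reported birth weight, and limit the conclusion on trajectory to net weight change since birth.

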The purpose of this study is to evaluate a proposed malnutrition screening scheme for infants - the infant Paediatric Yorkhill Malnutrition Screening(iPYMS)score to discover how well it distinguishes infants who are well-nourished from those undernourished or at risk of undernutrition (discriminant validity).

We also need to compare it with results of other reputable nutritional measurements (concurrent validity).

Hypotheses

1. Most infants with low fat levels or at high risk of undernutrition with Paediatric Global Nutritional Assessment (PGNA) will be identified by a high infant Yorkhill Malnutrition Score (sensitivity).
2. Infants with high infant Yorkhill Malnutrition Score will have lower fat levels than infants with low score (discriminant validity).
3. There will be a moderate to good agreement and concordance between infants who have been screened with iPYMS and STRONG kids.
4. Explore the utility of bioelectrical impedance and an infant eating behaviour scale in detecting infants with malnutrition
5. Relate the malnutrition risk to length of hospital stay

Method

The researcher will pilot the study and this will be the opportunity receive feedback on the study design. The researcher will first complete the iPYMS scoring sheet for each

child and then the questionnaires (SGNA and Infant EBQ) will be completed by the main carer of patient.

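### Does the and/or wording for the reference standard leave the sensitivity and specificity of iPYMS undefined?

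*Protocol*

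**What the plan says.** Three parts of the protocol bear on this.

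- **Analysis-Statistics.** The iPYMS result is to be "cross-tabulated with the respective nutrition risk from the Paediatric Subjective Global Nutrition Assessment or, body composition assessment". The next two sentences define false negatives (at risk by the reference, missed by iPYMS) and false positives (low risk by the reference, high on iPYMS). Both use the bracket "according to body composition assessment and/or the Paediatric Subjective Global Nutrition Assessment".
- **Hypotheses, item 1.** The infants whom iPYMS should detect are described as "Most infants with low fat levels or at high risk of undernutrition with Paediatric Global Nutritional Assessment (PGNA"), with a plain *or* between the two criteria.
- **Method.** Accuracy is described as how well the tool performs in "detecting infants who really have problems and correctly identifying those who do not (sensitivity and specificity").

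No sentence says how to class an infant who is positive on one reference and negative on the other.

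**The concern.** Sensitivity and specificity need a reference that splits infants into two classes that do not overlap and leave nobody out. The same and/or on both classes does not guarantee that once the references are pooled. Reading it as *or* on both sides makes a discordant infant at risk by one reference and low risk by the other, so the infant is counted twice. Reading it as *and* on both sides drops that infant. The two classes are then complements only if the references never disagree.

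At stake is Hypothesis 1, together with the specificity that the Method section asks for. If several readings were equally open, the most flattering could be picked once the data are in. Hypotheses 2 to 5 and the sample size do not depend on this wording.

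**Working it through.** **1. The logic.** Let *b* be the share positive on both references, *d* the share discordant and *n* the share negative on both, with *b + d + n* = 1.

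| Reading | At risk | Low risk | Sum |
|---|---|---|---|
| *or* on both classes | b + d | d + n | 1 + d |
| *and* on both classes | b | n | 1 − d |
| either v neither | b + d | n | 1 |
| both v not both | b | d + n | 1 |
| one table per reference | positive on that reference | negative on that reference | 1 |

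The first two rows do not give a 2×2 table unless *d* = 0. The last three do, taking low risk as the complement of at risk.

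**2. Which rows the text supports.** The cross-tabulation sentence speaks of the respective risk from one reference or the other. Its natural meaning is one table per reference. If the references are pooled, the *or* of Hypothesis 1 gives *b + d* as the at-risk class, and the Method section's contrast makes the low-risk class the remainder, *n*. That is either v neither. No section requires both references to be positive before an infant counts as at risk, and Hypothesis 1 says otherwise, so both v not both is unsupported. The first two rows conflict with the Method section.

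**3. Inputs for the size.** The protocol gives no accuracy figure to reproduce.

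- From the protocol: 200 infants; one third high on iPYMS, from "three equal groups of patients with different undernutrition scores (low, medium, high").
- Assumed: each reference flags a share *p* of 0.1, 0.2 or 0.3. The protocol gives 10–30% only as one overall expectation.
- Assumed: kappa *k* between the references of 0.2, 0.4 or 0.6; iPYMS high in 80% of both-positive and 50% of discordant infants.

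Formulas, unweighted in the infants assessed:

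- d = 2p(1 − p)(1 − k); b = p − d/2; n = 1 − b − d
- iPYMS-high share in both-negative infants: s₀ = (1/3 − 0.8b − 0.5d)/n
- Either v neither: Se = (0.8b + 0.5d)/(b + d); Sp = 1 − s₀
- One reference: Se = (0.8b + 0.25d)/p; Sp = 1 − (0.25d + n·s₀)/(1 − p)

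**4. Worked case, p = 0.2, k = 0.4.**

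- d = 2 × 0.2 × 0.8 × 0.6 = 0.192 (38.4 infants); b = 0.2 − 0.096 = 0.104 (20.8); n = 0.704 (140.8)
- s₀ = (0.3333 − 0.0832 − 0.096)/0.704 = 0.219
- Either v neither: Se = 0.1792/0.296 = 60.5%; Sp = 78.1%
- One reference: Se = 0.1312/0.2 = 65.6%; Sp = 1 − 0.2021/0.8 = 74.7%

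The supported readings differ by 5.1 points in sensitivity and 3.4 in specificity.

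**5. All nine settings** (Se/Sp in %, gaps in points).

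| p | k | Positive on either | One reference | Either v neither | Gap Se / Sp |
|---|---|---|---|---|---|
| 0.1 | 0.2 | 17.2% | 58.4/69.5 | 54.9/71.1 | 3.5 / 1.7 |
| 0.1 | 0.4 | 15.4% | 63.8/70.1 | 59.0/71.3 | 4.8 / 1.3 |
| 0.1 | 0.6 | 13.6% | 69.2/70.7 | 64.1/71.5 | 5.1 / 0.9 |
| 0.2 | 0.2 | 32.8% | 60.8/73.5 | 56.6/78.0 | 4.2 / 4.5 |
| 0.2 | 0.4 | 29.6% | 65.6/74.7 | 60.5/78.1 | 5.1 / 3.4 |
| 0.2 | 0.6 | 26.4% | 70.4/75.9 | 65.5/78.2 | 4.9 / 2.3 |
| 0.3 | 0.2 | 46.8% | 63.2/79.5 | 58.5/88.8 | 4.7 / 9.3 |
| 0.3 | 0.4 | 42.6% | 67.4/81.3 | 62.3/88.1 | 5.1 / 6.9 |
| 0.3 | 0.6 | 38.4% | 71.6/83.1 | 66.9/87.6 | 4.7 / 4.5 |

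Sample Selection states: "We expect that malnutrition will be identified in between 10-30% of infant studied". In the five settings where at most 30% are positive on either reference, the specificity gap is 1–3 points.

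**6. Dependence on the 50% assumption.** With iPYMS high in 70% of discordant infants, the case p = 0.3, k = 0.2 becomes impossible (s₀ is negative). In the other eight settings the sensitivity gap falls to 1–2 points and the specificity gap becomes 2–12.

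**7. Scale.** With 40 reference-positive infants and 32 detected, the 95% Wilson interval for sensitivity is 65–90%.

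**The case for a change.** The strongest case for a change is that the protocol itself writes the error definitions, so this is not simply detail left to a later document, and that and/or does permit pooling. In the worked case, *and* on both classes gives 80% sensitivity and 78% specificity, the higher value on each measure, because it drops the 38 discordant infants. Both v not both gives 80%/72% against 61%/78% for either v neither. Over the nine settings those two complementary rules differ by 13–25 points in sensitivity and 2–15 in specificity.

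The logic stands, and so does the remark that the bracket is careless. The size does not carry over. The 13–25 points need a both-positive rule that Hypothesis 1 contradicts. They also rest on the assumed 50%: at 70% the sensitivity gap falls to 4–8 points, although the specificity gap widens. Dropping discordant infants would show at once, since the two denominators would sum to about 162 rather than 200.

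Writing out separate tables would not close every gap either. The protocol does not say whether one or all of triceps skinfold, subscapular skinfold and MUAC must lie below −2 SD, and the SGNA categories are not shown. An analysis plan can settle such details. Content shared between SGNA and iPYMS, and the use of one researcher for both, are separate cautions that do not bear on how the classes are defined.

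**Conclusion.** The repeated and/or is a wording slip that the rest of the protocol resolves. An analyst following the text would tabulate iPYMS against each reference separately or, for a composite, compare infants positive on either with infants negative on both. Both give proper 2×2 tables. Under the assumed flag rates, kappa and iPYMS rates, the two differ by about 4–5 points in sensitivity and 1–9 in specificity; the specificity figure rises to 12 if iPYMS is high in 70% of discordant infants. The difference is between two estimands, each answering a fair question, and is not a bias in one of them. Spelling the rule out would be a courtesy to the reader, but the plan needs no change.

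### Sensitivity and specificity are read from an unweighted table of infants who were chosen by their iPYMS score, so sensitivity is overstated and specificity understated

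*Protocol*

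**What the plan says.** The protocol makes accuracy an aim. Hypothesis 1 states that most infants with low fat levels or at high risk on the global assessment "will be identified by a high infant Yorkhill Malnutrition Score (sensitivity"), and the Method section adds the tool's performance in "correctly identifying those who do not (sensitivity and specificity"). A positive screen is defined in the section on development of the tool: "a score of 2 or more reflects a high risk of undernutrition".

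Who receives the reference assessments depends on that same score. The Method section says "We will study all screen positive and a sample of screen negative infants". Sample Selection says "Quota sampling will be used to obtain three equal groups of patients with different undernutrition scores (low, medium, high"), and then gives fractions: the majority of high scorers, every third medium scorer, and "Every tenth child screened at low risk of undernutrition". High scorers are expected to be only 10–20% of all patients.

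Analysis-Statistics cross-tabulates iPYMS risk against the global assessment or body composition. The proportion of reference-positive patients "who were not identified by the iPYMS will be recorded as false negatives" (that is, 1 − sensitivity), and the proportion of reference-negative patients scored high is recorded as false positives (1 − specificity). The section also says "K-statistics will be used for Agreement of the methods". It mentions no weighting or other allowance for the sampling.

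**The concern.** Sensitivity and specificity are proportions within reference status. They can be read from a cross-table only if inclusion in the table does not depend on the test result. Here it does, by design, which is partial-verification bias. Malnourished infants whom the tool misses sit in the low and medium score groups, which are thinned to roughly a tenth and a third, while those it detects sit in the high group, which is kept mostly or wholly intact. The false-negative cell is therefore too small relative to the true-positive cell, and the true-negative cell too small relative to the false-positive cell.

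At stake is the answer to Hypothesis 1. The table could show that most malnourished infants are identified when, on the wards, the tool misses more than half of them.

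**Working it through.** The protocol states no expected sensitivity or specificity, so there is no figure of its own to reproduce.

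**Inputs from the protocol.** High scorers 10–20% of patients; sampling fractions above 1/2 and up to 1 (high), 1/3 (medium), 1/10 (low); alternatively three equal groups; a positive test is a high score.

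**Assumed inputs.** The protocol does not give the medium and low shares or the reference-positive rate at each score level. The illustration uses shares *p* of 15% high, 25% medium and 60% low, and reference-positive rates *d* of 40%, 10% and 3%.

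**Direction.** With *f* the fraction assessed, and *f*(not high) its average over the relevant medium and low scorers:

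- table odds of sensitivity = true odds × *f*(high) / *f*(not high)
- table odds of specificity = true odds × *f*(not high) / *f*(high)

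High scorers are taken at more than 1/2, the others at 1/3 and 1/10, so the ratio always exceeds 1. With all high scorers taken it lies between 3 and 10. A true sensitivity of 50% (odds 1) then reads 75% to 91%, and a true specificity of 90% (odds 9) reads 75% down to 47%. The direction never reversed in 200,000 random scenarios with the high-score fraction between 0.5 and 1.

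**True values in the illustration.**

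- Reference-positive, *p* × *d*: 0.060 + 0.025 + 0.018 = 0.103. Sensitivity = 0.060/0.103 = 58.3%.
- Reference-negative, *p* × (1 − *d*): 0.090 + 0.225 + 0.582 = 0.897. Specificity = (0.225 + 0.582)/0.897 = 90.0%.

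**Table with three equal groups.**

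- Sensitivity = 0.40/(0.40 + 0.10 + 0.03) = 75.5%.
- Specificity = (0.90 + 0.97)/(0.60 + 0.90 + 0.97) = 75.7%.

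**Table with fractions 1, 1/3, 1/10, per 1,000 screened.** Assessed: 150, 83.3 and 60. Reference-positive: 60, 8.33 and 1.8.

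- Sensitivity = 60/70.13 = 85.6%.
- Specificity = (75 + 58.2)/(90 + 75 + 58.2) = 59.7%.
- If only 60% of high scorers are assessed: 36/46.13 = 78.0% and 133.2/187.2 = 71.2%.

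**Weighting restores the truth.** With weights 1, 3 and 10, the reference-positive counts become 60, 25 and 18, and 60/103 = 58.3%.

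**Range.** High share 10% or 20%, medium 20% or 30%, and reference-positive rates of 40/10/3%, 50/15/5% or 60/20/10% in high/medium/low:

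| | True | Table, equal groups | Table, fractions 1, 1/3, 1/10 |
|---|---|---|---|
| Sensitivity | 33–68% | 67–75% | 70–90% |
| Specificity | 86–95% | 76–81% | 50–77% |

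In the six cases with 10% high scorers, true sensitivity is 33–49%, while the equal-group table still shows 67–75%.

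**If medium also counted as positive.** True sensitivity 0.085/0.103 = 82.5% reads 0.50/0.53 = 94.3% with equal groups; true specificity 0.582/0.897 = 64.9% reads 0.97/2.47 = 39.3%. The direction is the same.

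**Other summaries.** The proportion malnourished is 10.3% in the illustration but 0.53/3 = 17.7% in an equal-group sample. Kappa also depends on the mix of scores in the sample; its bias was not quantified.

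**The case against.** The direction of the bias is not in dispute. The case against runs as follows.

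- *The protocol does not say the table is unweighted, and the SAP may deal with it.* True as to wording. But Analysis-Statistics states the table and the proportions to be taken from it, so this is a stated rule that gives a wrong result. The correction also needs counts of infants screened but not assessed at each score level, and the protocol does not provide for recording them.
- *The sizes are assumed, and the main illustration does not overturn Hypothesis 1.* Correct: 58% is still most. Among the illustrative cases with high scorers at 10% or 20% of admissions, the answer reverses only at 10%. The direction follows from the protocol; the exact size does not.
- *Equal groups and the stated fractions are different schemes.* This stands. For the assumed mix the fractions give groups of about 51%, 28% and 20%, not thirds. Both schemes bias the table in the same direction, and the fractions bias it more.
- *The study is sized for skinfold differences between score groups, which this sampling does not bias.* Also true, as it is for reference-positive rates within a score level. Sensitivity is still Hypothesis 1.
- *The kappa and prevalence points are thin.* Fair. The expected 10–30% malnourished refers to infants studied, so it can be read as a description of the sample. These points are secondary.
- *Weighting assumes that assessed infants represent their score level.* This stands as a limitation. Recruitment notes that most children go home on the first day while assessment is aimed at the next, so those assessed may be sicker than others with the same score.

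**Conclusion.** The analysis is wrong as written and must be changed. Selection by iPYMS score followed by uncorrected proportions overstates sensitivity and understates specificity whenever high scorers are assessed at a higher rate than the rest, as the protocol requires. In the main illustration, sensitivity is overstated by 17 points with equal groups and 27 with the stated fractions, and specificity is understated by 14 and 30. These sizes rest on assumed score shares and reference-positive rates; the direction does not. The oversampling itself is sound, and the skinfold comparisons can stand.

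**What to change.** Leave the sampling as it is, but reconcile the equal-group quota with the stated fractions. Then:

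1. Keep a log, from the first day of recruitment, of the number screened and the number fully assessed at each iPYMS level, with reasons for non-assessment such as early discharge.
2. Estimate sensitivity, specificity and the false-negative and false-positive proportions with each infant weighted by screened/assessed in its iPYMS level (Begg–Greenes or inverse-probability weighting). Use achieved fractions, not nominal ones.
3. Give confidence intervals that reflect the weighting (bootstrap or survey-type).
4. Apply the same weights to kappa and to any statement of the proportion malnourished. Show the unweighted table only as a description of the sample. Predictive values within a score level need no weighting.

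The cost is a tally and one analysis step. The sensitivity will look less favourable and be less precise. In the main illustration with 67 per group, its sampling SD is 9.6 points weighted against 6.7 unweighted. With the stated fractions and 200 infants (about 102, 57 and 41) it is about 11 against 5. Few low scorers will be reference-positive: at 3%, the chance of seeing none is 0.97^67 = 13% with 67 low scorers and 0.97^41 = 29% with 41, so the interval method must cope with an empty cell.
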